2 SYNOPSIS

Sponsor: CoLucid Pharmaceuticals, Inc.
Name of Finished Product: Lasmiditan
Name of Active Ingredient: Lasmiditan
Study Title: A Phase I, Randomized, Double-Blind, Placebo-Controlled, 5-Period, Cross-Over Study Assessing the Effects of Lasmiditan on Simulated Driving Performance in Normal Healthy Volunteers
Study Number: COL MIG-106
Study Phase: Phase 1
Primary Objective: 
To determine the effects of acute doses of lasmiditan 50 mg, 100 mg and 200 mg compared to placebo and positive control (alprazolam 1.0 mg) on simulated driving performance in healthy subjects as measured by standard deviation of lateral position (SDLP) using the Cognitive Research Corporation Driving Simulator-MiniSim (CRCDS-MiniSim).
Secondary Objective: 
To determine the effects of lasmiditan 50 mg, 100 mg, and 200 mg compared to placebo and positive control (alprazolam 1.0 mg) on other measures of simulated driving performance (e.g., speed deviation, lane exceedance and other measures of lane position and speed control, cornering, collisions, and divided attention [DA]), CogScreen Symbol Digit Coding (SDC) test, and self-report measures (i.e., Karolinska Sleepiness Scale (KSS), Visual Analog Scales (VAS) addressing motivation and performance, and if the subject feels safe to drive).

Sponsor: CoLucid Pharmaceuticals, Inc.
Name of Finished Product: Lasmiditan
Name of Active Ingredient: Lasmiditan
Endpoints: Primary Endpoint: 
• SDLP Secondary Endpoints: 
• Sleepiness Endpoint - KSS• Self-reported readiness to drive (“Right now do you feel safe to drive?”)• VAS to assess subject’s motivation and self-appraisal of their driving performance• Performance Endpoints
▪ CogScreen SDC test
○ CogScreen SDC test○ Number of correct responses○ Response Accuracy○ Standard deviation of reaction time• Driving Performance Endpoints
▪ Lane exceedance; including number, maximum, duration, and area of exceedance▪ Ratio above speed limit, excessive speed count, excessive speed ratio▪ Average speed, speed deviation, speed count, speedings ratio▪ Excessive Ay (cornering speed threshold exceeded)▪ Collision count, off-road crashes, total collisions▪ DA: Correct Responses, Omission Errors, Commission Errors, Reaction Time, Standard Deviation of Reaction Times• Single-dose plasma drug levels and driving performance
Study Design: 
This will be a randomized, single dose, double-blind, placebo-controlled, Latin-square design with 5-period (full) crossover study with subjects randomized to treatment sequences. Subjects will complete all 5 Periods within the treatment sequence that they are randomized to.
 
Treatments:
 
• Treatment A: Lasmiditan 50 mg• Treatment B: Lasmiditan 100 mg• Treatment C: Lasmiditan 200 mg• Treatment D: Alprazolam 1 mg

Sponsor:
CoLucid Pharmaceuticals, Inc.

Name of Finished Product:
Lasmiditan

Name of Active Ingredient:
Lasmiditan

- Treatment E: Placebo

Subjects will be randomized equally into one of ten treatment sequences:

Treatment Sequence	Period 1	Period 2	Period 3	Period 4	Period 5
1	A	B	E	C	D
2	B	C	A	D	E
3	C	D	B	E	A
4	D	E	C	A	B
5	E	A	D	B	C
6	D	C	E	B	A
7	E	D	A	C	B
8	A	E	B	D	C
9	B	A	C	E	D
10	C	B	D	A	E

Each Period will be approximately 5 days in duration (5-7 days).

Study drug will be administered by site staff on Day 1 of each Period. Subjects will wear a blindfold when taking each dose to maintain the blind. The tablet size and shape are deemed similar enough to maintain the blind with a blindfolded subject.

Testing is conducted 1.5 hours post-dose (on Days 1, 7, 14, 21, and 28 of each Period).

Schematic of Design:

Period 1 → Washout 1 → Period 2 → Washout 2 → Period 3 → Washout 3 → Period 4 → Washout 4 → Period 5 → EOS
Day 1 Days 2-6 Day 7 Days 8-13 Day 14 Days 15-20 Day 21 Days 22-27 Day 28 Day 35

A sufficient number of subjects will be enrolled to complete 80 healthy volunteers in the 5-period crossover study. The washout between Periods will be at least 5 days. Subjects will be evaluated following a single dose.

The positive control (alprazolam 1.0 mg) is included to establish the sensitivity of the study endpoints to detecting residual sedation.

Screening (Visit 1) will include procedures as described in the Schedule of Activities and further in the protocol. Prior to randomization, subjects will be screened for simulator sickness and will receive standardized training on the driving simulator and cognitive test battery. Screening procedures and screening assessments may be performed on different days but must be

Sponsor: CoLucid Pharmaceuticals, Inc.
Name of Finished Product: Lasmiditan
Name of Active Ingredient: Lasmiditan
completed within 28 days before Period 1 (Visit 2). The Familiarization and Practice drives on the driving simulator must be completed no more than 21 days prior to Period 1. Treatments within each Period Subjects will return to the site where, according to the randomization schedule, they will be assigned and dosed with study medication (lasmiditan, alprazolam or placebo). Prior to dosing (the evening of clinical research unit [CRU] admission) they will complete a 20-minute practice drive on the CRCDS-MiniSim and a practice trial on the CogScreen SDC test. Within approximately 85 minutes of dosing, subjects will perform the CogScreen SDC Test, KSS, and indicate their self-perceived safety to drive. Subjects will then perform the Country Vigilance-Divided Attention (CVDA) driving scenario on the CRCDS-MiniSim commencing approximately 90 minutes (1.5 hours) post-dosing. Upon completion of the driving scenario subjects will be administered a VAS to assess subject's motivation and self-appraisal of their driving performance. Subjects will leave the clinical site at approximately 24-hour post-dose. Blood draws for pharmacokinetics will be taken during the Periods predose and approximately 155 minutes (-15 to +30 minutes) post-dose. The total duration of subject participation will be approximately 5 weeks (range 5-7 weeks).
Subject Population: Inclusion Criteria: 
1. Able and willing to voluntarily consent to participate in this study and provide written informed consent prior to start of any study-specific procedures.2. Males and females between the ages of 21 and 50 years of age (inclusive). No more than 60% of one gender will be enrolled on the study.3. Body Mass Index (BMI) between 18 and 32 kg/m² (inclusive).4. Subject is able to reliably perform study assessments (SDLP no higher than 1 standard deviation greater than the mean for normal healthy adults completing the practice scenario; SDC Correct no less than 1 standard deviation below the mean for healthy adults in their age range); demonstrates the ability to understand task instructions, and is physically capable (e.g., adequate manual dexterity, vision, and hearing) and cognitively capable of performing study tasks.5. Subject possesses a valid driver's license and is an active driver. Drives a minimum of 10,000 miles (about 16,000 km) per year for the previous 3 years.

Sponsor: CoLucid Pharmaceuticals, Inc.
Name of Finished Product: Lasmiditan
Name of Active Ingredient: Lasmiditan

6. Subject must also demonstrate simulator sickness questionnaire scores which are not indicative of simulator sickness as defined in the driving simulation operations manual.7. Subject has a regular sleep pattern, are not engaged in shift-work, and in general, have at least 7 hours of sleep each night (bedtime occurs between 21:00 and 24:00 hours).8. Subject has a score < 10 on the Epworth Sleepiness Scale.9. Use of a medically highly effective form of birth control during the study and for thirty (30) days:
a. A female volunteer must meet one of the following criteria:
i. If of childbearing potential – agrees to use one of the accepted contraceptive regimens from at least 28 days prior to the drug administration, during the study and for at least 60 days after the dose. An acceptable method of contraception includes one of the following:
ii. Abstinence from heterosexual intercourseiii. Systemic contraceptives (birth control pills, injectable/implant/insertable hormonal birth control products, transdermal patch)iv. Intrauterine device (with or without hormones)v. Condom with spermicide or condom with intra-vaginally applied spermicidevi. If of non-childbearing potential – should be surgically sterile (i.e. has undergone complete hysterectomy, bilateral oophorectomy, or tubal ligation) or in a menopausal state (at least one year without menses)b. A male volunteer with sexual partners who are pregnant, possibly pregnant, or who could become pregnant must meet the following criteria:
i. Participant is unable to procreate, defined as surgically sterile (i.e. has undergone a vasectomy within at least the last 6 months)ii. Participant is apt to procreate and agrees to use one of the accepted contraceptive regimens from first drug administration until 3 months after the drug administration. An acceptable method of contraception

Sponsor: CoLucid Pharmaceuticals, Inc.
Name of Finished Product: Lasmiditan
Name of Active Ingredient: Lasmiditan

includes one of the following:
 
iii. Abstinence from heterosexual intercourse.iv. Condom with spermicide or condom with intra-vaginally applied spermicide 
c. A male volunteer agrees to refrain from sperm donation from drug administration until 3 months after the drug administration.
 
10. Subjects who are willing and able to comply with scheduled visits, treatment plan, laboratory tests, and other study procedures.
 
Exclusion Criteria:
 
1. History or presence of clinically significant cardiovascular, pulmonary, hepatic, renal, hematological, gastrointestinal, endocrine, immunologic, neurological, oncologic, or psychiatric disease or any other condition that, in the opinion of the Investigator, would jeopardize the safety of the subject or the validity of the study results.2. A history within 2 years of, or current treatment for a sleeping disorder (including excessive snoring, obstructive sleep apnea), or a chronic painful condition that interferes with the subject's sleep.3. A history of difficulty in falling asleep or staying asleep in the previous 3 months, that is considered clinically significant by the investigator.4. Subject has a history or diagnosis of any of the following conditions:
a. Primary or secondary insomniab. Narcolepsyc. Cataplexy (familial or idiopathic)d. Circadian Rhythm Sleep Disordere. Parasomnia including nightmare disorder, sleep terror disorder, sleepwalking disorder, and rapid eye movement behavior disorderf. Sleep-related Breathing Disorder (obstructive or central sleep apnea syndrome, central alveolar hypoventilation syndrome)g. Periodic Limb Movement Disorderh. Restless Legs Syndromei. Primary Hypersomnia

Sponsor: CoLucid Pharmaceuticals, Inc.
Name of Finished Product: Lasmiditan
Name of Active Ingredient: Lasmiditan

j. Excessive Daytime Sleepiness (EDS)k. Subject has visual or auditory impairment which in the opinion of the investigator would interfere with study related procedures or study conduct. 
5. Expected to use any other medication or dietary supplement to promote sleep including over-the-counter sleep medications, during their participation in the study.6. Subject consumes excessive amounts of coffee, tea, cola, or other caffeinated beverages per day. Excessive amount is defined as greater than 6 servings (1 serving is approximately equivalent to 120 mg of caffeine)7. Subject has traveled across 1 or more time zones (transmeridian travel) in the last 2 weeks prior to randomization or is expected to travel across 1 or more time zones during the study.8. Expected to work on a rotating shift during their participation in the study.9. Subject works a night shift.10. History or presence of seizure disorder.11. History of urinary retention, angle closure glaucoma, or increased ocular pressure.12. History of gastrointestinal tract surgery, except appendectomy.13. Has abnormal finding on the physical exam, medical history, electrocardiogram (ECG), or clinical laboratory results at Screening, that are considered clinically significant by the investigator.14. Presence of out-of-range cardiac interval (PR < 110 msec, PR > 200 msec, QRS < 60 msec, QRS > 110 msec and QTc > 440 msec) on the screening ECG or other clinically significant ECG abnormalities15. History of orthostatic hypotension, fainting spells, or blackouts, that are considered clinically significant by the investigator.16. The presence of chronic or acute infections, that are considered clinically significant by the investigator.17. History of allergy/hypersensitivity (including drug allergies) that are deemed relevant to the study as judged by the Investigator.18. Use of psychoactive prescription or non-prescription medications, psychoactive nutritional supplements or herbal preparations within 2 weeks or 5 half-lives (whichever is longer) of admission to the CRU on Day 1.19. Has received any previous study drug within 30 days prior to the first dose of this study drug.

Sponsor: CoLucid Pharmaceuticals, Inc.
Name of Finished Product: Lasmiditan
Name of Active Ingredient: Lasmiditan

20. Is a smoker of more than 10 cigarettes or eCigarettes, or 3 cigars or 3 pipes per day, and is unable to refrain from smoking while confined to the CRU.21. Has any history of dependency or treatment for substance abuse within the past 2 years.22. Subject with a history of alcoholism or who consumes excessive amounts of alcohol, defined as greater than 3 glasses of alcoholic beverages (1 glass is approximately equivalent to: beer [284 mL/9 ounces], wine [125 mL/4 ounces], or distilled spirits [25 mL/1 ounce]) per day.23. Subjects who consume alcohol on a regular basis (i.e., ≥ 5 times/week) before bedtime will be excluded from the study.24. Inability to comply with the dietary regimen of the clinical research center.25. Pregnancy / positive pregnancy test.26. Planning to become pregnant during the study or within 30 days of study completion.27. Inability to use adequate contraception (as defined in item 9 of the Inclusion Criteria) during the study. It is recommended that adequate contraception be used for 1 month following completion of the study.28. Has a positive screen for alcohol or other drugs of abuse (amphetamines, methamphetamines, barbiturates, benzodiazepines, cocaine, cannabinoids, opiates).29. Has a history for Hepatitis B, Hepatitis C, or Human Immunodeficiency Virus (HIV) at Screening or has been previously treated for Hepatitis B, Hepatitis C, or HIV.
Planned Number of Subjects: A sufficient number of subjects will be enrolled to ensure completion of 80 subjects.
Test Product; Dose; and Mode of Administration: Lasmiditan 50, 100, and 200 mg tablets and alprazolam 1.0 mg tablets will be provided for the study by the Sponsor. The subjects will be instructed to swallow the tablets whole, with approximately 240 mL of water. Study drug will be administered by qualified unblinded CRU personnel and a mouth check performed.
Duration of Treatment: The total duration of study participation will be approximately 5 weeks (5-7 weeks).
Safety Assessments:

Sponsor: CoLucid Pharmaceuticals, Inc.
Name of Finished Product: Lasmiditan
Name of Active Ingredient: Lasmiditan
Adverse Events: Adverse events (AEs) will be captured from the time of obtaining informed consent until discharge from the study.
Pregnancy Test: A serum pregnancy test will be done at screening and end of study for females of child-bearing potential. A serum pregnancy test will also be collected at each CRU check-in for females of child-bearing potential. A positive pregnancy test at any time during the study will automatically disqualify the subject from further participation in the trial.
Serum Chemistries, Hematology and Urinalysis: Blood will be collected for serum chemistries and hematology and urine will be collected for urinalysis at the following visits: 
• Screening,• Day 35 or end of study (EOS).
Vital Signs: Vital signs (blood pressure and heart rate) will be collected at the following visits/time points: 
• Screening,• Day -1, 6, 13, 20, and 27 upon clinic check-in,• Day 1, 7, 14, 21, and 28 prior to dosing and at 70 minutes (prior to CogScreen testing) post morning dose. Temperature will be measured at Screening and Day 35 or End of Study.
Electrocardiogram Twelve-lead ECG recording will be collected at Screening and Day 35 or EOS prior to discharge.
Pharmacokinetic (PK) Blood Sampling: Lasmiditan: Blood samples for the determination of plasma lasmiditan concentrations will be drawn at the following time points following each lasmiditan or placebo dose: 
• Days 1, 7, 14, 21, and 28 pre-dose• Days 1, 7, 14, 21, and 28 at 155 minutes (-15 to +30 minutes) post-dose
Statistical Plan and Methods:

Sponsor: CoLucid Pharmaceuticals, Inc.
Name of Finished Product: Lasmiditan
Name of Active Ingredient: Lasmiditan
Safety: 
Safety analysis will be based on all subjects enrolled who receive at least 1 dose of the study medication. The safety analysis will evaluate adverse events and additional safety parameters. The number and percentage of subjects experiencing at least one AE will be summarized by body system, preferred term, and treatment. If appropriate, AEs will also be summarized by intensity and relationship to study drug. SAEs, if any, will be tabulated.
 
Additional safety parameters will be assessed from summaries of physical examinations, 12-lead ECGs and vital signs. The 12-lead ECG results will be categorized as normal, clinically significant abnormal, and not clinically significant abnormal. Hematology, chemistry and urinalysis laboratory test results will be categorized relative to the normal ranges. The changes from baseline for each of these parameters at post-dose time points will be presented. Complete listings and summary tables for all safety information including AEs, laboratory safety data, ECG, vital signs and physical examination will be included in the study report.

Pharmacokinetics: 
The decision as to which plasma samples collected will be assayed for evaluation of pharmacokinetics/pharmacodynamics will be determined by CoLucid Pharmaceutical, Inc. The relationship between single-dose and steady-state plasma drug levels and driving performance will be evaluated, data permitting. If indicated, these samples may also be assayed and/or pooled for assay in an exploratory manner for metabolites and/or additional pharmacodynamic markers.

Pharmacodynamics: 
The primary end point, SDLP, will be analyzed using a mixed model with fixed effects for sequence, period, and treatment, and a random effect for subject within sequence.
 
Secondary endpoints will be evaluated similarly, however Lane Exceedance will be log transformed (more specifically $\ln(x+1)$) prior to analyses. Pair-wise comparisons for readiness to drive will be analyzed using McNemar test.

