8 SUBJECT DEFINITION

Individuals are eligible for this study if they meet all inclusion and no exclusion criteria. The criteria below will be assessed at the Screening visit. Continued eligibility will be assessed by serum pregnancy and screens for alcohol and drugs of abuse on Days -1, 6, 13, 20, and 27.

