8.1 Inclusion Criteria

1. Able and willing to voluntarily consent to participate in this study and provide written informed consent prior to start of any study-specific procedures.
2. Males and females between the ages of 21 and 50 years of age (inclusive). No more than 60% of one gender will be enrolled in the study.
3. Body Mass Index (BMI) between 18 and 32 kg/m² (inclusive).
4. Subject is able to reliably perform study assessments (SDLP no higher than 1 standard deviation greater than the mean for normal healthy adults completing the practice scenario; SDC Correct no less than 1 standard deviation below the mean for healthy adults in their age range); demonstrates the ability to understand task instructions, and is physically capable (e.g., adequate manual dexterity, vision, and hearing) and cognitively capable of performing study tasks.
5. Subject possesses a valid driver's license and is an active driver. Drives a minimum of 10,000 miles (about 16,000 km) per year for the previous 3 years.
6. Subject must also demonstrate simulator sickness questionnaire scores which are not indicative of simulator sickness as defined in the driving simulation operations manual.
7. Subject has a regular sleep pattern, are not engaged in shift-work, and in general, have at least 7 hours of sleep each night (bedtime occurs between 21:00 and 24:00 hours).
8. Subject has a score < 10 on the Epworth Sleepiness Scale.
9. Use of a medically highly effective form of birth control during the study and for thirty (30) days:
 - a. A female volunteer must meet one of the following criteria:
 - i. If of childbearing potential – agrees to use one of the accepted contraceptive regimens from at least 28 days prior to the drug administration, during the study and for at least 60 days after the dose. An acceptable method of contraception includes one of the following:
 - ii. Abstinence from heterosexual intercourse
 - iii. Systemic contraceptives (birth control pills, injectable/implant/insertable hormonal birth control products, transdermal patch)

- iv. Intrauterine device (with or without hormones)
 - v. Condom with spermicide or condom with intra-vaginally applied spermicide
 - vi. If of non-childbearing potential – should be surgically sterile (i.e. has undergone complete hysterectomy, bilateral oophorectomy, or tubal ligation) or in a menopausal state (at least one year without menses)

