8.2 Exclusion Criteria

1. History or presence of clinically significant cardiovascular, pulmonary, hepatic, renal, hematological, gastrointestinal, endocrine, immunologic, neurological, oncologic, or psychiatric disease or any other condition that, in the opinion of the Investigator, would jeopardize the safety of the subject or the validity of the study results.
2. A history within 2 years of, or current treatment for, a sleeping disorder (including excessive snoring, obstructive sleep apnea), or a chronic painful condition that interferes with the subject's sleep.
3. A history of difficulty either falling asleep or staying asleep in the previous 3 months, that is considered clinically significant by the investigator.
4. Subject has a history or diagnosis of any of the following conditions:
 - a. Primary or secondary insomnia
 - b. Narcolepsy
 - c. Cataplexy (familial or idiopathic)

- d. Circadian Rhythm Sleep Disorder
 - e. Parasomnia including nightmare disorder, sleep terror disorder, sleepwalking disorder, and rapid eye movement behavior disorder
 - f. Sleep-related Breathing Disorder (obstructive or central sleep apnea syndrome, central alveolar hypoventilation syndrome)
 - g. Periodic Limb Movement Disorder
 - h. Restless Legs Syndrome
 - i. Primary Hypersomnia
 - j. Excessive Daytime Sleepiness (EDS)
 - k. Subject has visual or auditory impairment which in the opinion of the investigator would interfere with study related procedures or study conduct.
5. Expected to use any other medication or dietary supplement to promote sleep including over-the-counter sleep medications, during their participation in the study.
 6. Subject consumes excessive amounts of coffee, tea, cola, or other caffeinated beverages per day. Excessive amount is defined as greater than 6 servings (1 serving is approximately equivalent to 120 mg of caffeine)
 7. Subject has traveled across 1 or more time zones (transmeridian travel) in the last 2 weeks prior to randomization or is expected to travel across 1 or more time zones during the study.
 8. Expected to work on a rotating shift during their participation in the study.
 9. Subject works a night shift.
 10. History or presence of seizure disorder.
 11. History of urinary retention, angle closure glaucoma, or increased ocular pressure.
 12. History of gastrointestinal tract surgery, except for appendectomy.

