 13. Has abnormal finding on the physical exam, medical history, electrocardiogram (ECG), or clinical laboratory results at Screening, that are considered clinically significant by the investigator.
 14. Presence of out-of-range cardiac interval (PR < 110 msec, PR > 200 msec, QRS < 60 msec, QRS > 110 msec and QTc > 440 msec) on the screening ECG or other clinically significant ECG abnormalities
 15. History of orthostatic hypotension, fainting spells, or blackouts, that are considered clinically significant by the investigator.
 16. The presence of chronic or acute infections, that are considered clinically significant by the investigator.

17. History of allergy/hypersensitivity (including drug allergies) that are deemed relevant to the study as judged by the Investigator.
18. Use of psychoactive prescription or non-prescription medications, psychoactive nutritional supplements or herbal preparations within 2 weeks or 5 half-lives (whichever is longer) of admission to the CRU on Day -1.
19. Has received any previous study drug within 30 days prior to the first dose of this study drug.
20. Is a smoker of more than 10 cigarettes or eCigarettes, or 3 cigars or 3 pipes per day, and is unable to refrain from smoking while confined to the CRU.
21. Has any history of dependency or treatment for substance abuse within the past 2 years.
22. Subject with a history of alcoholism or who consumes excessive amounts of alcohol, defined as greater than 3 glasses of alcoholic beverages (1 glass is approximately equivalent to: beer [284 mL/9 ounces], wine [125 mL/4 ounces], or distilled spirits [25 mL/1 ounce]) per day.
23. Subjects who consume alcohol on a regular basis (i.e., ≥ 5 times/week) before bedtime will be excluded from the study.
24. Inability to comply with the dietary regimen of the clinical research center.
25. Pregnancy / positive pregnancy test.
26. Planning to become pregnant during the study or within 1 month of study completion.
27. Inability to use adequate contraception (as defined in item 9 of the Inclusion Criteria) during the study. It is recommended that adequate contraception be used for 30 days following completion of the study.
28. Has a positive screen for alcohol or other drugs of abuse (amphetamines, methamphetamines, barbiturates, benzodiazepines, cocaine, cannabinoids, opiates).

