12.2 Routine Reporting

For the purposes of this study, the period of observation of AEs extends from the screening visit until the follow-up call. During this period, all AEs spontaneously reported by the subject, observed by the clinical staff, or elicited by general questioning will be recorded and reported in the CRF.

Any AE which remains unresolved as of the last visit will require an evaluation and follow-up until the AE has been resolved or a reasonable explanation for its persistence found, or is deemed mild and safely resolving.

In the case of AEs deemed related to the Investigational Product, every effort will be made to determine the final outcome.

It is the Investigator's responsibility to ensure subjects experiencing AE receive appropriate follow-up, treatment where required, and that every action is well documented.

Subjects will be questioned on their health status at the beginning of study period and before departure from the clinical site. Open-ended questions will be asked.

Subjects will be questioned on their health status at the beginning of the study period and before the departure from the clinical site. Open-ended questions will be asked.

Classification will be performed by System Organ Class (SOC) and Preferred Term (PT) using the Medical Dictionary for Regulatory Activities (MedDRA), version 19.0 or higher.

In general, AEs occurring secondary to other events (eg, clinical sequelae or a cascade of events) should be identified by their primary cause. For example, if severe vomiting is known to result in dehydration, it is sufficient to record only vomiting as SAE or AE in the CRF. However, medically significant AEs occurring secondary to an initiating event that are separated in time should be recorded as independent events on the CRF.

Pregnancy in a female subject on the study shall be reported to the sponsor within 24 hours of the knowledge of its occurrence by the Principal Investigator or designee (for pregnancies occurring during the course of the study or immediately following the end of the study). Because of the possibility that the fetus/embryo could have been exposed to the study drug through the parent and for the subject's safety, the pregnancy will be followed up to determine its outcome, including spontaneous or voluntary termination, details of birth, presence or absence of any birth defects, congenital anomalies, or maternal and/or newborn complications.

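### The exclusion criteria cover pregnancy, planned pregnancy and contraception but not breastfeeding, so nursing does not by itself make a woman ineligible (low severity)

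*Protocol*

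**What the plan says.** Protocol section 8 sets the rule: "Individuals are eligible for this study if they meet all inclusion and no exclusion criteria". Section 8.1 admits both sexes from age 21 to 50 and caps either at 60% of enrolment.

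Three exclusions concern reproduction, and they have the same scope in the synopsis and in section 8.2:

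- Item 25: "Pregnancy / positive pregnancy test".
- Item 26: "Planning to become pregnant during the study or within 30 days of study completion" in the synopsis, and "Planning to become pregnant during the study or within 1 month of study completion" in section 8.2.
- Item 27: "Inability to use adequate contraception (as defined in item 9 of the Inclusion Criteria) during the study", followed by a recommendation to continue contraception for a month (synopsis) or 30 days (section 8.2) after the study.

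Inclusion 9 adds contraception rules for women and men and a bar on sperm donation. Exclusion 1 is the general clause. It leaves to the investigator any condition that "would jeopardize the safety of the subject or the validity of the study results". Section 12.2 explains why a pregnancy is followed to its outcome: it is possible that "the fetus/embryo could have been exposed to the study drug through the parent".

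**The concern.** The plan takes several steps to keep study drug away from offspring before birth and none that concern a nursed infant. Subjects are healthy volunteers, so no therapeutic benefit to the mother offsets a risk to her child. Lasmiditan is still in development, and section 6.1 names dizziness and fatigue as its most commonly reported adverse events. Alprazolam is in the trial because it is expected to show sedation. An infant exposed through milk would be a third party who has not consented. The question is whether any existing rule keeps a nursing woman out and, if none does, how much exposure the design could produce.

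**Working it through.** No figure in the plan bears on this point, so the check is a reading of the text and a count of doses.

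**1. Does any rule exclude a nursing woman?**

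| Provision | What it covers | Does it require exclusion for nursing? |
|---|---|---|
| Exclusions 25–27 (synopsis, 8.2) | Pregnancy, planned pregnancy, contraception | No |
| Inclusion 9 (synopsis, 8.1) | Contraception, sperm donation | No |
| Exclusion 1 (8.2) | Investigator's view of subject safety or validity of results | No; the infant is not the subject, though validity leaves room for judgement |
| Exclusion 3 (8.2) | Clinically significant difficulty falling or staying asleep | No; may apply to some nursing women |
| Exclusion 13 (8.2) | Abnormal findings judged clinically significant | No; lactation is not an abnormal finding |
| Inclusion 7 (8.1) | Regular sleep, in general at least 7 hours a night | No; makes nursing a newborn unlikely |
| Continued eligibility (8, 10.2.1) | Serum pregnancy, alcohol and drug screens | No; a pregnancy test does not identify nursing |
| Concurrent medication and lifestyle (11.16, 11.17) | Medicines, alcohol, caffeine, exercise, caution on driving | No |
| Discharge (10.2.2) | Leave about 24 hours after dosing; longer stay if the physician thinks it necessary | No |
| SAP | Analysis | No mention |

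Under the section 8 rule, a nursing woman who meets everything else is eligible.

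**2. How many active doses would she receive?** Each of the ten sequences in section 9.1 contains A, B, C, D and E exactly once. A completer therefore has 5 dosing days:

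- 3 lasmiditan (50, 100 and 200 mg)
- 1 alprazolam (1 mg)
- 1 placebo

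Active days = 5 − 1 = 4, falling among Days 1, 7, 14, 21 and 28.

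**3. How many women are in the trial?** Assume the 60% cap holds among the 80 planned completers. The number of women then lies between 0.40 × 80 = 32 and 0.60 × 80 = 48. The documents do not say how many might be nursing, and the sleep criterion and overnight stays suggest few.

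**4. What limits infant exposure?** Sections 6.3.1 and 10.2 have subjects admitted the day before dosing and discharged about 24 hours after it. That is 2 nights per period, or 2 × 5 = 10 nights over the trial. No provision is described for an infant in the unit, so direct nursing in the first day after a dose is unlikely (an inference, not a stated rule). Two routes remain open: milk expressed in the unit, and nursing after discharge. The plan states no half-life for either drug and no data on passage into milk; sections 6.2.1 and 6.2.2 refer to the Investigator's Brochure and the Package Insert. An exposure per infant cannot be derived from the documents.

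**The case against.** The strongest reply is that the practical risk is small and investigators already have the means to deal with it. Exclusion 1 extends to anything that threatens the validity of the results, and night waking to nurse plausibly does so in a study of sleepiness and driving. Inclusion 7 and exclusion 3 point the same way, and section 11.18 lets the investigator remove a subject for any reason. Ten nights in the unit would deter many nursing mothers. Consent pages are not available for review and may address the matter. All of this stands as a limit on likelihood. None of it requires exclusion, and consent wording would not change the eligibility criteria.

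A reader might infer three stronger things that the documents do not support:

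- *That the infant could be exposed on all five dosing days.* Every sequence includes placebo, so there are four active days.
- *That a nursing woman must be accepted.* Section 8 says who is eligible. It does not oblige a site to enrol anyone, and the discretion above is real.
- *That the protocol contradicts itself, because section 12.2 recognises exposure through the parent.* That sentence gives a reason for following up a pregnancy. Extending it to milk is a fair analogy, but it shows a gap in coverage and not an inconsistency.

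**Conclusion.** The omission is real and appears in both copies of the criteria, so it is not a copying slip. Breastfeeding does not by itself make a woman ineligible. A nursing completer would receive four active single doses, with confinement and the sleep criterion reducing the chance that her infant is exposed without removing it. The size of the risk cannot be stated: it is an unquantified possibility affecting few subjects. The conclusion assumes that the supplied protocol and SAP text holds all the eligibility rules. Severity is low, since the primary endpoint, sample size and analyses are unaffected. The case for acting rests on protecting a third party who cannot consent, in a study with no therapeutic benefit, at almost no cost.

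**What to change.** Amend exclusion 25 in both the synopsis and section 8.2 by adding the words *or breastfeeding* after "Pregnancy / positive pregnancy test". Confirm it at Screening through the medical and social history that sections 10.1 and 11.10 already require.

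The cost is one phrase in a protocol amendment and no new procedure. The downside is possibly a very few more screen failures. The SAP needs no change.
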